#### **Confidentiality Statement**

## 7.2 Biomarkers

### 7.2.1 CYP2A6

CYP2A6 activity is calculated in plasma as the metabolic ratio of trans-3' hydroxycotinine and cotinine, both expressed in molar equivalent (nmol/L) (Jacob et al, 2011):

$$\text{CYP2A6} = \frac{\text{HCOT[ng/mL]} \times 5.202}{\text{COT[ng/mL]} \times 5.675}$$

The conversion factor will be applied as follows:

Cotinine (COT)

The molecular weight is 176.2178 g/mol (Chemical Information Specialized Information Services RN:486-56-6) Therefore to transform COT from ng/mL to nmol/L, the result in ng/mL will be multiplied by 5.675

Trans-3'hydroxycotinine (HCOT)

The molecular weight is 192.217 g/mol (Chemical Information Specialized Information Services RN:34834-67-8) Therefore to transform HCOT from ng/mL to nmol/L, the result in ng/mL is multiplied by 5.202

The ratio will be reported as a percentage.

## 7.3 Questionnaires

### 7.3.1 VAS Craving Assessments

A VAS-craving assessment will be used to assess the level of craving of the subject based on their response to the question, "How strong is your craving for cigarettes?" on a scale of 0 (no craving) to 10 (strong craving).

The VAS craving will be completed by the subject at Days 1 to 4. For the fixed puffing regimen the first assessment will be done 15 minutes  $\pm$  5 minutes prior to  $T_0$  fix, all other assessments will be done after  $T_0$  fix, at 4 minutes  $\pm$  2 minutes, at 10 minutes  $\pm$  2 minutes, at 15 minutes  $\pm$  2 minutes, 30 minutes  $\pm$  5 minutes, 1 hour, 2 hours, 4 hours  $\pm$  10 minutes each.

For the *ad libitum* use period the first assessment will be done 15 minutes  $\pm$  5 minutes prior to  $T_0$  ad lib, all other assessments will be done after  $T_0$  ad lib, at 10 minutes  $\pm$  2 minutes, at 20 minutes  $\pm$  2 minutes, 30 minutes  $\pm$  5 minutes, 40 minutes  $\pm$  5 minutes, 1 hour, 2 hours, 4 hours  $\pm$  10 minutes each.

For the VAS craving score  $AUC_{VAS}$  will be derived for each puffing regimen ( $AUC_{VAS\ fix\ (0-4h)}$  and  $AUC_{VAS\ ad\ lib\ (0-4h)}$ ) using trapezoidal rule.

#### Confidentiality Statement

Data and information contained in this document are considered to constitute trade secrets and confidential commercial information, and the legal protections provided to such trade secrets and confidential information are hereby claimed under the provisions of applicable law. No part of this document may be publicly disclosed without the written consent of Philip Morris Products S.A.

The actual VAS assessments times post-exposure collected in the CRF will be used in the computation of the AUCVAS, with the exception of pre-exposure assessment time which will be considered as time zero ( $T_0$  fix or  $T_0$  ad lib).

### 7.3.2 Fagerström Test for Nicotine Dependence

The FTND questionnaire will be used in its revised version (Heatherton et al, 1991) as updated in 2012 (Fagerström et al, 2012). The FTND questionnaire consists of 6 items as presented in Table 7. These questions are to be answered by the subject themselves. It is conducted at Screening only, to determine subject's dependence on nicotine.

**Table 7 Scoring for the Fagerstrom Test for Nicotine Dependence**

FTND Question	Response	Score
1 How soon after you wake up do you smoke your first cigarette?	

▪ After 60 minutes

▪ 31-60 minutes

▪ 6-30 minutes

▪ Within 5 minutes

	0 1 2 3
2 Do you find it difficult to refrain from smoking in places where it is forbidden?	

▪ No

▪ Yes

	0 1
3 Which cigarette would you hate most to give up?	

▪ The first one in the morning

▪ Any other

	1 0
4 How many cigarettes per day do you typically smoke?	

▪ 10 or less

▪ 11-20

▪ 21-30

▪ 31 or more

	0 1 2 3
5 Do you smoke more frequently during the first hours after waking than during the rest of the day?	

▪ No

▪ Yes

	0 1
6 Do you smoke if you are so ill that you are in bed most of the day?	

▪ No

▪ Yes

	0 1

The FTND total score will be derived by summing the individual item scores if all items are non-missing, otherwise the total score will be set to missing.

For the FTND total score, descriptive statistics and frequency tables according to the following classification will be provided (Fagerström et al, 2012):

FTND total score	Classification value
0 - 3	Mild
4 - 6	Moderate
7 - 10	Severe

### 7.3.3 Adapted Modified Cigarette Evaluation Questionnaire

The adapted mCEQ will be completed by the subject him/herself daily (within 60 minutes after the end of the *ad libitum* use period) from Day 1 to Day 4 to assess the degree to which subjects experience the reinforcing effects of P3P use by measuring:

- Product satisfaction (satisfying, tastes good, enjoy the product);
- Psychological rewards (calms down, more awake, less irritable, helps concentrate, reduces hunger);
- Aversion (dizziness, nausea);
- Enjoyment of respiratory tract sensations (single-item assessment);
- Craving reduction (single-item assessment)

The questionnaire to be used adapts the wording of mCEQ items (Cappelleri et al, 2007) to RRP, following a similar approach with the Product Evaluation Scale (Hatsukami et al. 2013) which is an adaptation of the mCEQ for oral tobacco products.

The adapted mCEQ consists of 12 items as presented in Table 8. Items are assessed on a 7-point scale, ranging from 1 (not at all) to 7 (extremely). Higher scores indicate greater intensity on that scale.

**Table 8 Adapted mCEQ - Questions and Subscales**

Question	Subscale
1 Was it satisfying?	Product Satisfaction
2 Did it taste good?	Product Satisfaction
3 Did you enjoy the sensation in your throat and chest?	Enjoyment of Respiratory Tract Sensations
4 Did it calm you down?	Psychological Reward
5 Did it make you feel more awake?	Psychological Reward
6 Did it make you feel less irritable?	Psychological Reward
7 Did it help you concentrate?	Psychological Reward
8 Did it reduce your hunger for food?	Psychological Reward
9 Did it make you dizzy?	Aversion
10 Did it make you nauseated?	Aversion
11 Did it immediately relieve your craving for a cigarette?	Craving Reduction
12 Did you enjoy it?	Product Satisfaction

The subscales scores will be derived by averaging the relevant individual non-missing item scores if at least 50% are non-missing, otherwise the subscale score will be set to missing.

### 7.3.4 Sensory Questionnaire

The sensory questionnaire (Rose et al. 2010) will be completed by the subject him/herself daily (within 60 minutes after the end of the *ad libitum* use period) from Day 1 to Day 4 after each product use to assess the subject's opinion on the following sensory parameters:

- Puff information i.e., how they liked the puffs, harshness of puffs, and similarity to own brand;
- Strength of puffs on tongue, nose, mouth, windpipe and chest.

The sensory questionnaire consists of 8 items as presented in Table 9. Items are assessed on a 7-point scale, ranging from 1 (not at all) to 7 (extremely). Higher scores indicate greater intensity on that scale.

**Table 9 Sensory Questionnaire - Questions**

Question
1 How much did you like the puffs you took?
2 How harsh were the puffs you took?
3 How similar to your own brand were the puffs?
4 Strength of puffs on tongue?
5 Strength of puffs in nose?
6 Strength of puffs in back of mouth & throat?
7 Strength of puffs in windpipe?
8 Strength of puffs in chest?

Each item will be analyzed individually (no subscales).

### 7.3.5 Cough Assessment

Subjects will be asked if they have experienced a regular need to cough (e.g., coughing several times) in the last 24 hours prior to assessment. If the answer is 'yes', they will be asked to complete a visual analogue scale (VAS), three Likert scale questions and an open question assessing their cough during previous 24 hours.

The VAS will assess how bothersome cough is to the subject ranging from 'not bothering me at all' to 'extremely bothersome', and this will be given a numeric value between 0 and 100.

Subjects will also be asked to assess the intensity and frequency of cough and the amount of sputum production on Likert scales as presented in Table 10.

**Table 10 Cough Assessment Likert Scales**

Question	Likert Scale
1 How intense is your cough?	1 = very mild 2 = mild 3 = moderate 4 = severe 5 = very severe
2 How frequently do you normally have to cough each day?	1 = rarely 2 = sometimes 3 = fairly often 4 = often 5 = almost always
3 To what extent do you produce sputum when coughing?	0 = no sputum 1 = a moderate amount of sputum 2 = a larger amount of sputum 3 = a very large amount of sputum

Cough assessment will be conducted at Admission prior to product test and 24 hours ( $\pm 1$  hour) after product use ( $T_0$  fix) for each variant (Day 2 through Day 5). Cough assessment should be done in the morning prior to any product use.

## 7.4 Human Puffing Topography

The following Human Puffing Topography Parameters will be measured per-puff:

**Table 11 Human Puffing Topography Parameters Per-Puff**

Description	Variable	Unit
Puff number	Ni	
Puff volume	Vi	mL
Puff duration	Di	ses
Average puff flow	Qmi	mL/sec
Peak flow	Qci	mL/sec
Inter puff interval	li	sec
Sum of li and Di	DFi	sec
Peak flow position	PosQci	%
Number of peaks	Pn	

The following Human Puffing Topography Parameters will be calculated per-product use experience:

**Table 12 Human Puffing Topography Parameters Per-Product Use**

Description	Variable	Formula	Unit
Total number of puffs	NPC	$\Sigma N_i$	
Total puff volume	TVOL	$\Sigma V_i$	mL
Average puff volume	AvgVi	$\Sigma V_i / NPC, i=1 \dots NPC$	mL
Average puff duration	AvgDi	$\Sigma D_i / NPC, i=1 \dots NPC$	sec
Total puff duration	TDi	$\Sigma D_i$	sec
Average use flow	AvgQmi	$\Sigma Q_{mi} / NPC, i=1 \dots NPC$	mL/sec
Average peak flow	AvgQci	$\Sigma Q_{ci} / NPC, i=1 \dots NPC$	mL/sec
Total inter puff interval	Tli	$\Sigma I_i$	sec
Average inter puff interval	Avgli	$\Sigma Q_{ci} / NPC, i=1 \dots NPC$	sec
Total puffing duration	TDFi	$\Sigma D_{fi}$	sec
Puffing Intensity	SMINT	TVOL/TDFi	mL/sec
Puffing Time Index	PTI	$100 * TDi / TDFi$	%
Puff Frequency	PFeq	$NPC / (TDFi / 60)$	

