6.2.2 Investigational Period (Day 1 to Day 5)

Each subject will use P3P 3 on Day 1. In the morning of Day 2, subjects will be randomized to one of six sequences in order to cross-over to the use of P3P 1, P3P 2 and P3P 4 on Days 2, 3 and 4 (section 6.3).

On each assessment day (Day 1 to Day 4), following at least 10 hours of abstinence from any tobacco and nicotine containing products, subjects will use the assigned product for the given visit with two product use regimen as described in Figure 2:

- using a fixed puffing regimen comprising of 12 puffs in total at a rate of one inhalation every 30 seconds (\pm 5 seconds) in the morning.
- using *ad libitum* use period for 60 minutes (\pm 5 minutes) in the afternoon.

A puffing topography device will be attached to each P3P. There will be one recording of HPT parameters per product. Each P3P product will be weighed before and after product use to estimate the amount of nicotine delivered in the aerosol. During the *ad libitum* use period, the subjects can use the product according to their puffing behavior, without restrictions in the number of puffs, interpuff interval duration or number of products used. The number of P3P products used during the *ad libitum* use period will be recorded. The start and stop time of each product used during each puffing regimen will be recorded as well as the total number of puffs taken at the fixed puffing regimen.

The start of product use for fixed puffing and for the *ad libitum* use period will be defined as T_0 fix and T_0 ad lib, respectively. There will be a washout period of 10 hours between T_0 fix and T_0 ad lib.

There will be no product use on the Discharge day (Day 5).

Except for the assigned products, subjects will not be allowed to use any nicotine-containing products through Discharge or early termination.

Subjects will be continuously supervised by the investigational site staff during P3P use.

Confidentiality Statement

Data and information contained in this document are considered to constitute trade secrets and confidential commercial information, and the legal protections provided to such trade secrets and confidential information are hereby claimed under the provisions of applicable law. No part of this document may be publicly disclosed without the written consent of Philip Morris Products S.A.

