7.9 Other Study Procedures

7.9.1 Human Puffing Topography

Human puffing topography involves the measurement of each subject's unique way of using P3P using the HPT SODIM® device. The HPT SODIM® device, model SPA/M (SODIM® Instrumentation, Fleury les Aubrais, France) is a device which is used to measure puffing topography. It consists of a special sample holder with mechanical adapter and a data logger. Both the sample holder and the mechanical adapter are associated prior the activation of the P3P, and its insertion into the mechanical adapter using a depth adjustment tool. The sample holder is connected by 2 narrow tubes to the portable data logger/recording system. Any malfunction of the HPT SODIM® portable device will be documented in the appropriate log.

The HPT SODIM® device has to be used for every P3P used for all subjects from Day 1 to Day 4, both during the fixed puffing and the *ad libitum* use period. For each subject, one HPT Device will be assigned at Day 1 which will be used by that subject for all HPT assessments. A replacement device will be provided in case of malfunction of the device assigned.

The Sponsor will provide training on the use of the HPT SODIM® device to the site collaborators which will be responsible for the HPT assessment. All HPT SODIM® devices will be returned to the Sponsor after completion of the study.

The HPT SODIM® device measures and records the flow rate and other per-puff parameters listed in Appendix D. From the per-puff parameters, per-product use experience parameters, representing average or total values per product, will be derived (Appendix D).

Prior to calculation of the per-product use experience parameters, the Sponsor's HPT group will process, validate and discard any invalid data, as per the Sponsor's SOPs. The Sponsor will provide copies of both the raw and validated HPT datasets to the Investigator. Only valid data for the per-puff and per-product use experience parameters will be part of the study database and will be analyzed.

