Appendix D – Human Puffing Topography Parameters

Table D1 Per-puff parameters

Description	Variable	Unit
Puff number	Ni	
Puff volume	Vi	mL
Puff duration	Di	s
Average flow [Vi/Di]	Qmi	mL/s
Peak flow	Qci	mL/s
Inter puff interval	li	s
Sum of li and Di	DFi	s
Peak flow position	PosQci	%
Number of peaks	Pn	

Table D2 Per-product use experience parameters

Description	Variable	Formula	Unit
Total number of puffs	NPC	Σ Ni	
Total puff volume	TVOL	Σ Vi	mL
Average puff volume	AvgVi	Σ Vi / NPC, i=1 ... NPC	mL
Average puff duration	AvgDi	Σ Di / NPC, i=1 ... NPC	s
Total puff duration	TDi	Σ Di	s
Average flow	AvgQmi	Σ Qmi / NPC, i=1 ... NPC	mL/s
Peak flow	AvgQci	Σ Qci / NPC, i=1 ... NPC	mL/s
Total inter puff interval	Tli	Σ li	s
Average inter puff interval	Avgli	Σ li / NPC, i=1 ... NPC	s
Total puffing duration	TDFi	Σ DFi	s
Puffing Intensity	SMINT	TVOL/TDFi	mL/s
Puffing Time Index	PTI	(100*TDi)/TDFi	%
Puff Frequency	PFeq	NPC/(TDFi/60)	

Confidentiality Statement

Data and information contained in this document are considered to constitute trade secrets and confidential commercial information, and the legal protections provided to such trade secrets and confidential information are hereby claimed under the provisions of applicable law. No part of this document may be publicly disclosed without the written consent of Philip Morris Products S.A.

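### SAP Table 12 computes the average inter-puff interval from peak flow, so one per-product topography variable would be a flow labelled as seconds

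*SAP*

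**What the plan says.** SAP Section 7.4 has two tables. Table 11 lists the variables measured for each puff, among them "Inter puff interval" (li, sec) and peak flow (Qci, mL/sec). Table 12 gives the formulas for the values calculated per product use.

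In Table 12, the row "Average inter puff interval" (Avgli, sec) carries the formula "\Sigma Q_{ci} / NPC, i=1 \dots NPC". The row "Average peak flow" (AvgQci, mL/sec) carries the same formula.

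For the same parameter, protocol Appendix D, Table D2, has "Σ li / NPC, i=1 ... NPC". The entries visible in the SAP's list of changes from the protocol (Section 9) do not mention topography.

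The denominator NPC is labelled "Total number of puffs". Both documents write it as the sum of Ni, where Ni is the puff number.

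Per-product parameters belong to the endpoint of secondary objective 3. SAP Section 12.6.3 summarises them by variant for both use regimens.

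**The concern.** The numerator of an average interval has to be a sum of intervals. The SAP row sums peak flows, so its formula disagrees with its own label, its own unit, the variable list one table earlier and the protocol. The SAP presents Table 12 as the way these parameters will be calculated, so a programmer who follows it would implement the wrong variable.

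At stake is one reported variable for each variant and regimen, in Tables 15.2.4.14 and 15.2.4.16 and the matching listings. SAP Table 21 appears to flag both tables for topline review, which takes place before the full set of outputs is complete.

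**Working it through.** The documents state no numerical result for this variable, so there is none to reproduce. The check compares the formulas and then works one example.

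**Step 1: formulas and units.**

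| Source | Parameter | Formula | Unit of formula | Unit in row |
|---|---|---|---|---|
| SAP Table 12 | AvgQci | ΣQci / NPC | mL/sec | mL/sec |
| SAP Table 12 | Avgli | ΣQci / NPC | mL/sec | sec |
| Protocol Table D2 | Avgli | Σli / NPC | s | s |

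NPC is a count and has no unit, so the unit of each average is that of its numerator. The SAP row for Avgli is the only one of the three that fails.

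**Step 2: worked example.** Protocol Section 6.2.2 sets a "fixed puffing regimen comprising of 12 puffs in total at a rate of one inhalation every 30 seconds". The documents give no puff duration D or peak flow Q. I assume D = 1 to 3 s, Q = 20 to 80 mL/s, puffs that start 30 s apart, and one interval recorded for each of the 12 puffs.

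- Each interval is li = 30 − D.
- Protocol formula, D = 1 s: (12 × 29) / 12 = 348 / 12 = 29 s.
- Protocol formula, D = 3 s: (12 × 27) / 12 = 324 / 12 = 27 s.
- SAP formula, Q = 20 mL/s: (12 × 20) / 12 = 240 / 12 = 20, printed as seconds.
- SAP formula, Q = 80 mL/s: (12 × 80) / 12 = 960 / 12 = 80, printed as seconds.

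The SAP result does not depend on the interval at all. The assumed flow range includes the true interval of 27 to 29, so a wrong value could look plausible in a table.

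**Step 3: reach.** Of the 13 rows in Table 12, none takes Avgli as an input. The total inter-puff interval (Tli) is written as the sum of the intervals, so the correct mean can be recovered as Tli / NPC. The total volume, puff duration and puffing duration, the puffing intensity and the puffing time index use neither Avgli nor NPC.

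**The case against.** **The formula may be an artefact of text extraction.** Other formulas in the SAP also read oddly. In Section 13.1.3.2 the three micro rate constants show one and the same expression, and small symbol and unit slips occur in Tables 11 and 12. A repeated formula would fit that pattern, so the printed page is worth a look. However, the row directly above, for the total interval, reads correctly, and nothing shows that the Avgli row was altered.

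**The error may never reach the results.** Protocol Section 7.9.1 derives these parameters from Appendix D, where Avgli is right, and the sponsor's topography group validates the data first. That stands as a mitigation. It does not settle which document the programmer follows, and the two conflict.

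**A reader might infer that the puff count is wrong too.** Taken literally, summing ordinal puff numbers over 12 puffs gives 1 + 2 + ... + 12 = 78. The documents do not support this. The row is labelled as the number of puffs, and the averages run from i = 1 to NPC. With NPC = 78 they would call for 78 − 12 = 66 puffs that do not exist. This is loose notation for a count.

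**A reader might also infer that the protocol's own mean interval is too low**, because 12 puffs have 11 gaps between them. Both documents treat the interval as a per-puff variable and do not say what is recorded after the last puff. The recording convention is unstated, and no error is shown.

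**Conclusion.** The Avgli row of SAP Table 12 is wrong as written. Programmed from the SAP, Avgli would equal AvgQci exactly and report a flow as a time. The size of the error depends on the peak flow, which the documents do not give; the figures in the worked example rest on assumed ranges.

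The consequence is limited. One variable is affected, it is summarised descriptively with no model or contrast, and its correct value can be recovered from Tli and NPC. The finding does not extend to the other Table 12 variables or to the primary PK analysis. The wording of NPC and the handling of the last interval need clarification but are not shown to give wrong results. The conclusion assumes that the printed SAP page shows the formula as it reads here.

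**What to change.** In SAP Table 12, set Avgli = ΣIi / NPC, as in protocol Table D2.

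In the same edit, make two clarifications in both documents:

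- State that NPC is the count of valid puffs, not a sum of ordinal puff numbers. A count is needed because Section 7.9.1 of the protocol discards invalid data before the per-product values are calculated.
- State what is recorded as the interval after the last puff, and whether it enters the sum and the divisor.

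The cost is a text correction, plus a check that any existing program for Avgli uses the interval variable. No data collection, sample size or other analysis changes.

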## 7.5 Categorical Variables

**Table 13 Categorical Variable Definitions**

Variable	Categories
BMI (kg/m  )	Underweight: < 18.5 Normal range: $\geq 18.5$ and $< 25.0$ Overweight: $\geq 25.0$ and $< 30.0$ Obese: $\geq 30.0$
FTND total score	Mild: 0 - 3 Moderate: 4 - 6 Severe: 7 - 10
Adverse event relationship to investigational product	Related Not related
Adverse event relationship to study procedure	Related Not related
Adverse event expectedness	Not Expected Expected

**Table 13 Categorical Variable Definitions**

Variable	Categories
Action taken with investigational product due to adverse event	None Product Use Reduced Product Use Interrupted Product Use Stopped Not Applicable Unknown
Severity of adverse event	Mild Moderate Severe
Outcome of adverse event	Recovered/Resolved Recovered/Resolved With Sequelae Recovering/Resolving Not Recovered/Not Resolved Fatal Unknown
Seriousness criteria of adverse event	Fatal Life-threatening Requires hospitalization Results in disability/incapacity Congenital anomaly/birth defect Other medically important event
Action taken with investigational product due to product event	Product Replaced Product Withdrawn Other
Severity of product event	Minor Major

## 8 SAMPLE SIZE JUSTIFICATION

The sample size is empirically based, as there is no prior information on which to base it, and as there are no considerations for statistical hypothesis.

As per study design P3P 3 is the first product variant used by all subjects at Day 1 for safety reasons (i.e P3P 3 has the lowest nicotine concentration of all product variants). As a result, only the 3 remaining product variants will be randomized over Day 2-4, which leads to 6 possible sequences. Considering that this study is a pilot investigation, and that

